6.1.3. Primary target variable

The primary endpoint will be the change of best corrected visual acuity in ETDRS Letters score at month 12 when compared with baseline. This endpoint will be analysed by analysis of covariance (ANCOVA) with the baseline value as covariate (type II SS will be used since no interaction terms are included in the model).

The null hypothesis is:

$$H_0: \mu_{iDC} = \mu_{rDC}$$

and the alternative hypothesis is:

$$H_1: \mu_{iDC} \neq \mu_{rDC}$$

where μ_{iDC} is the mean of the differences in ETDRS Letters score between month 12 and baseline for the investigational arm (intensified diabetic control) and μ_{rDC} is the mean of the differences in ETDRS Letters score between month 12 and baseline for the control arm (regular diabetic control).

ITT population is used for the primary efficacy analysis. If no ETDRS Letter score is available at month 12 the closest measurement (could be before or after 12 month) which was at least after 3 months will be used for the analysis.

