4.2. Discussion of trial design, randomization and study arms

Selection bias is minimised by concealed random assignment of trial arms. Observer-masking (assessment of BCVA, macular thickness, capillary drop-out) is done to guard against *detection bias*. *Performance bias* is to be reduced by strict standardisation of trial procedures. *Attrition bias*

will be minimised by active follow-up of trial patients by a dedicated study nurse / physician (telephone, mail and in-person contact).

Randomisation of patients into two treatment arms will be performed centrally by CROLLL GmbH and will be computer-assisted, based on block-randomization lists. A randomization ratio of 1:1 will be used. No stratification is planned.

Patients will be randomized to one of the two study arms:

1. Regular Glycemic Control (Group 1): patients randomized into this group will be controlled by their general practitioner or private diabetologist (usual care). The glycemic control (blood measurements of HbA1c) will be performed at trial site (Department of diabetology, endocrinology and nutritional medicine) every 3 months. The site will not influence or change the diabetes medication given by general physician and serves as an observer only to monitor the diabetic control.
2. Intensified Glycemic Control (Group 2): patients randomized into this group will be controlled at the trial site (Department of diabetology, endocrinology and nutritional medicine) during first year monthly, in the second study year every 3 months. The individual HbA1c will be targeted according to the general status reflecting other risk factors for the vasculopathy (e.g. BMI, smoking, blood pressure, lipid status). All effort will be done to reach the target blood pressure $\leq 140/90$ mmHg and blood triglyceride level < 140 mg/dl: Further the patients will be educated to improve their eating habits in regard to reduce the carbohydrate intake.

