4.4. Withdrawal of trial subjects after trial start

Study subjects will be early discontinued from participation in the study if

- they withdraw consent from participating in the study
- no response to the ranibizumab treatment is observed, defined as persisting macular edema without any reduction of central retinal thickness after 3 consecutive monthly injections
- they present visual loss defined as ≥ 30 ETDRS Letters when compared with the baseline
- they develop vitreous bleeding due to active neovascularisation of the retina or optic disc confirmed by fluorescein angiography with need of surgical treatment (vitrectomy)
- any other clinical adverse event (AE), laboratory abnormality, illness or other medical condition or situation occurs that would not go along with the best interest of the patient in case of continuing the participation.

Note: Each patient should be followed-up even if the study treatment is discontinued.

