4.6.7. Blinding, Unblinding

Observer-masking (assessment of BCVA, macular thickness, capillary drop-out) is done to guard against detection bias. Unblinding procedures are not applicable (treatment is not blinded).

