4.6.8.1. Rescue therapy for emergencies

Rescue medication allowed in this study is panretinal and/or focal laser treatment (after 3 consecutive monthly injections) and only if a significant progression of neovascularization with associated threat of visual loss is seen. Laser treatment will be documented on the appropriate trial database/CRF pages.

The ranibizumab injection can be performed at the same day as a laser therapy, but not earlier than 30 minutes after laser treatment.

If the therapeutic effect will be considered insufficient by either the patient or the treating physician the patient may be withdrawn from the study and is able to receive whatever treatment is considered to be necessary.

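### For patients who leave early, a BCVA from about month 3 or 4 can stand as the month-12 primary value, and no analysis in the documents provided varies the missing-data assumption

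*Combined protocol and SAP*

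**What the plan says.** Section 6.1.3 makes the month-12 change in BCVA the primary endpoint, analysed by ANCOVA in the ITT population. If the month-12 score is missing, "the closest measurement (could be before or after 12 month) which was at least after 3 months will be used for the analysis".

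Three places govern who leaves and what happens next:

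- Section 4.4 opens its list with "Study subjects will be early discontinued from participation in the study if". The list includes "persisting macular edema without any reduction of central retinal thickness after 3 consecutive monthly injections", as well as a loss of 30 or more letters. It closes with "Note: Each patient should be followed-up even if the study treatment is discontinued".
- Section 4.6.8.1 adds: "If the therapeutic effect will be considered insufficient by either the patient or the treating physician the patient may be withdrawn from the study". Such a patient then "is able to receive whatever treatment is considered to be necessary".
- Section 4.2 says that attrition bias "will be minimised by active follow-up of trial patients by a dedicated study nurse / physician (telephone, mail and in-person contact"). Tables 2 and 3 schedule BCVA and OCT monthly to month 24.

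Section 4.6.7 states that "treatment is not blinded", but sections 3.5.3, 4.2 and 4.6.7 have BCVA and macular thickness assessed by masked observers.

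Section 6.1.6 plans two sensitivity analyses of the primary endpoint: the per-protocol (PP) population and a log transformation. Section 6.1.4 analyses BCVA and macular thickness by repeated measures under a stated MAR assumption, with LOCF for missing values. Section 6.1.8 allows no other imputation.

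**The concern.** The hypotheses in section 6.1.3 are about month-12 means. For a patient who leaves for good, the rule carries one earlier value forward and treats it as month 12. The thickness-response criterion acts after three monthly injections, close to the earliest time the rule accepts, so month 3-4 values are a realistic source. Because leaving is partly tied to poor response, these patients need not resemble those who stay. The assessors are masked, but the diabetes-control allocation is known to patients and treating physicians. Withdrawal for insufficient effect, which either of them may judge, could therefore differ by arm.

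Section 4.4 is also unclear. It ends study participation and then asks for follow-up when treatment stops, so a reader cannot tell whether scheduled BCVA continues for these patients. That decides how often the substitution rule is used.

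At stake is whether the final report could show that its conclusion does not depend on the substituted values. As written, it could not.

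**Working it through.** **Inputs from section 6.2:** difference 2.0 letters, SD 3.5, two-sided 5%, power 85%, 56 evaluable per arm, raised by about 7% to 60 per arm. The documents give no leaving rate by arm and no BCVA course from month 3 to month 12. Everything on those two points below is an assumption.

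**The plan's own figure.** The exact two-sample t-test (noncentral t) gives 56 per arm with power 85.0%, and 56 × 1.07 = 59.9, so 60. The plan's figure is reproduced. With 60 complete patients per arm, SE = 3.5 × √(2/60) = 0.639 and power is 87.4%.

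**Formula.** Let r and i be the patients substituted in the regular and intensified arms, G the further gain they would have had by month 12 apart from the treatment effect, and f the share of the 2.0-letter effect already present in the carried value. Then

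expected estimate = 2 + (r/60)·G − (i/60)·[G + (1 − f)·2]

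and, under no effect, bias = (r − i)·G/60.

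**Case 1: planned loss, balanced.** 7% of 60 is about 4 per arm, and G cancels.

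- f = 0: 2 − (4/60) × 2 = 1.87
- f = 0.5: 2 − (4/60) × 1 = 1.93
- No effect: bias 0

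**Power from attenuation alone** (7% substituted per arm, SE held at 0.639, estimate = 2 − 0.07 × (1 − f) × 2):

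| f | Estimate | Power |
|---|---|---|
| 0 | 1.86 | 82.3% |
| 0.25 | 1.895 | 83.7% |
| 0.5 | 1.93 | 85.0% |
| 0.75 | 1.965 | 86.2% |

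The fair comparator is the planned 85% with 56 evaluable per arm, because the plan does not count on 60 complete patients. The difference is at most about 3 points, and it is a gain of about 1 point at f = 0.75.

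**Case 2: the same 8 patients, unbalanced, with G = 2 (assumed).**

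| r / i | Estimate, f = 0 | Estimate, f = 0.5 | Bias if no effect |
|---|---|---|---|
| 6 / 2 | 2 + 0.20 − 0.13 = 2.07 | 2 + 0.20 − 0.10 = 2.10 | +0.13 |
| 2 / 6 | 2 + 0.07 − 0.40 = 1.67 | 2 + 0.07 − 0.30 = 1.77 | −0.13 |

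So the sign depends on which arm loses more patients and on how they would have changed.

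**Do the planned analyses test the rule?**

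- The log-transform analysis applies the same ANCOVA to the same substituted values.
- The PP set (section 6.1.1) requires at least 3 injections and an endpoint after 6 months of follow-up. It drops most month 3-6 substitutions, but only by selecting on events after randomisation, and it keeps later substitutions.
- The secondary repeated-measures analysis covers month 12, but with LOCF, which is nearly the same single-value substitution. MAR does not justify LOCF: it supports a likelihood-based model of the observed data, whereas LOCF assumes no change after the last visit.
- A patient with no score from month 3 onward has no primary value and, under section 6.1.8, is not imputed. That patient drops out of the ANCOVA, although section 6.1.1 describes the ITT set as having no exclusions.

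**Is a MAR-based analysis always better?** Take 7% per arm and f = 0.25. If the effect would have kept growing to 2.0, the closest value is biased by −0.07 × 0.75 × 2 = −0.105, and a correctly specified MAR analysis is about unbiased. If the effect stops growing once the patient leaves, the true mean difference is 1.895. The closest value is then unbiased, and the MAR analysis overstates by about 0.105. Neither approach is right under every course.

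**The case against.** The strongest reply is that the harm is small and already guarded against. Both arms receive the same ranibizumab regimen, the thickness-response criterion applies equally to both, and the assessors are masked. Active follow-up is planned, section 4.4 asks for follow-up after treatment stops, and BCVA is scheduled monthly, so most gaps should be filled from a neighbouring visit. The PP analysis removes most of the earliest substitutions. The trial is exploratory, and section 6.1 leaves further detail to a statistical analysis plan whose separate text is not among the documents.

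Most of this stands. It limits the likely size, and it limits the statement about missing sensitivity analyses to the documents provided. It does not answer two things. The substitution rule is already fixed in section 6.1.3 with no alternative beside it, and the follow-up that would make the rule harmless is left unclear by section 4.4 itself.

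A reader might infer that the primary result is seriously biased, or that the false-positive rate is materially raised. The documents do not support that: it needs substantial differences between arms in leaving or in later course, for which they give no figures. A reader might also infer that the closest-value ANCOVA must be replaced as the primary analysis. That does not follow either, because a MAR-based estimate is the worse one if vision stays flat or the effect stops growing after a patient leaves.

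**Conclusion.** The concern holds in limited form and should be fixed. The plan lets a month 3-4 BCVA stand for month 12 in patients whose leaving is partly tied to poor response, and nothing in the documents provided tests how far the result depends on that. At the planned loss, split evenly, the expected estimate falls from 2.0 to about 1.87-1.93 (0-50% of the effect present in the carried value), with no bias under the null. Power from attenuation alone is 82-86% (0-75% present), at an unchanged SE, against 85% planned. With 8 substituted patients split 6/2 or 2/6 and an assumed further gain of 2 letters, the null bias is +0.13 or −0.13 letters. Larger values need larger assumed differences between arms. If follow-up works as intended, the harm is small. Separately, stating MAR while imputing by LOCF in section 6.1.4 is inconsistent whatever the size of the loss.

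**What to change.** 1. **Primary endpoint (sections 6.1.3 and 6.1.6).** The closest-value ANCOVA can stay primary if the sponsor prefers. Pre-specify two sensitivity analyses:
   - a likelihood-based repeated-measures model, or multiple imputation, on all observed monthly BCVA to month 12, including values collected after withdrawal and patients with only pre-month-3 values. State that under MAR it describes leavers as if they had continued;
   - a delta-adjusted (tipping-point) analysis that shifts the imputed values by arm until the conclusion changes.

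   Report by arm how many values were substituted, from which month, and how many patients had none.
2. **Secondary BCVA and macular thickness (section 6.1.4).** Remove LOCF and fit the repeated-measures model to the observed data, in line with the stated MAR.
3. **Sections 4.4 and 4.6.8.1.** Reconcile ending study participation with follow-up after treatment stops, so that it is clear whether scheduled BCVA and OCT continue in patients who have not withdrawn consent. No treatment or stopping rule is proposed or changed.

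The cost is modest extra analysis and a protocol amendment to sections 6.1.3, 6.1.4, 6.1.6 and 4.4, with section 4.6.8.1 if its wording changes. Section 9 requires such changes to be written, reasoned and signed by all authors, and submitted where approval is needed. No new visits are needed, because BCVA and OCT are already monthly, and the sample size does not change.

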6.1.4. Secondary efficacy variables

Different statistical methods will be applied for analysis of secondary endpoints.

For the number of treatments at 6, 12, 18 and 24 months, an ANOVA without any covariates will be applied at each endpoint 6, 12, 18 and 24 months.

The data of change in BCVA and macular thickness at 6, 12, 18 and 24 months are analysed by repeated measures analysis of variance (assuming missing at random, MAR). The missing values for BCVA and macular thickness are imputed by the last observation carried forward (LOCF). The treatment by time interaction will be included in both statistical models but the baseline value will only be included in the change in BCVA analysis since the macular thickness will not be adjusted by the baseline value in this analysis.

The change in BCVA and macular thickness with respect to baseline values is calculated at 6, 12, 18 and 24 months. For each time point, the change values are described statistically by mean, standard deviation, and 95% confidence interval.

Time to reach target HbA1c is evaluated by log-rank test and hazard ratio in terms of a Cox proportional hazard model. The results are visualised by Kaplan-Meier curves. No covariates are included in the model.

The number of neovascular complications in two treatment arms is compared by frequencies and a chi-square test if applicable (the chi-squared test will not be used when the absolute frequency in any of the cells of the contingency table is below 5), otherwise the Fishers exact test will be performed.

ITT population is used for all secondary efficacy analyses.

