2.1. Rationale for the clinical trial

Several studies showed the significant reduction of DME after ranibizumab injections (Do et al. 2012, DRCR Network 2012). Patients could significantly increase their visual acuity under treatment and the safety profile is favourable compared to the application of intravitreal steroids. However, the treatment burden remains high, as ideally patients would receive monthly ranibizumab injections. This still provides a challenge for health care providers and patients alike.

Published studies showed that the intensive insulin treatment and diabetic control can reduce the risk of most retinopathy-related complications (Maple-Brown et al. 2012; Zhang X et al. 2014). However the most recently published meta-analysis could not confirm the reduction of prevalence of vision loss or blindness (Zhang X et al. 2014). Therefore further studies are needed to investigate the effect of intensive diabetic control on visual acuity. Our study is based on the hypothesis that an intensive insulin treatment will positively affect the visual acuity in patients with DME and reduce the need for re-treatment.

2.2. Primary objective / Hypothesis:

The trial investigates the influence of an intensified diabetes control programme on treatment of DME.

As a primary objective the change of best corrected visual acuity in ETDRS letters score at month 12 when compared with baseline (measured by the difference in ETDRS letters score between month 12 and baseline) will be evaluated.

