4.7.1.2. Secondary target variables

- Number of treatments with Ranibizumab up to 6, 12, 18 and 24 months of treatment respectively
- Mean average change in BCVA at 6, 12, 18 and 24 months after initial treatment
- Macular thickness (as measured with OCT) at 6, 12, 18, and 24 months after initial treatment
- Time to reach target HbA1c
- Number of neovascular complications: need for panretinal laser photocoagulation (PRP)
- Rates of ocular and of systemic AEs (retinal detachment, Central retinal artery occlusion, endophthalmitis; and rates of stroke, myocardial infarction, severe hypoglycemia)

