6.1.6. Sensitivity and Subgroup analyses

A sensitivity analysis for the primary endpoint based on the PP population will be performed.

Another sensitivity analysis will assess the influence of the assumption of normality for the primary analysis by transforming the data with the natural logarithm. The ANCOVA described in section 6.1.3 will be applied in the same way on the transformed data.

The primary and secondary endpoint except number of neovascular complications and rates of ocular and of systemic AEs will be analysed by descriptive statistics and statistical methods mentioned above within the following subgroups defined by the following potentially prognostic baseline variables:

- HbA1c: $\geq 9\%$
- HbA1c: $\geq 7,5\%$, $< 9\%$

- HbA1c: $\geq 6,5\%$, $< 7,5\%$
- Intravitreal treatment with ranibizumab before trial entry (yes vs no)
- Size of macula edema $>400\mu\text{m}$
- BCVA (>65 vs ≤ 65)

For the sake of subgroup analysis, the ITT population will be used.

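### The injection count is compared without covariates although four collected baseline variables are named as potentially prognostic; precision is likely lost if they jointly explain more than about 3.5% of its variance

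*Combined protocol and SAP*

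**What the plan says.** The count is a secondary endpoint, defined in section 4.7.1.2 as "Number of treatments with Ranibizumab up to 6, 12, 18 and 24 months of treatment respectively". Section 6.1.4 fixes its analysis: "an ANOVA without any covariates will be applied at each endpoint 6, 12, 18 and 24 months". No reason for leaving covariates out is given.

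Section 6.1.6 plans analyses "within the following subgroups defined by the following potentially prognostic baseline variables". The list has six bullets but four distinct variables: HbA1c (three bands), ranibizumab before trial entry, size of macular oedema, and BCVA. The endpoints covered are stated as follows: "The primary and secondary endpoint except number of neovascular complications and rates of ocular and of systemic AEs will be analysed". The injection count is not among the exceptions, so it is included. Nowhere is an overall comparison of the count adjusted for these variables.

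Three other places bear on the point:
- The synopsis, under statistical methods, names ANCOVA for comparing means between the two arms.
- Section 4.2 says of the randomisation: "No stratification is planned".
- Section 2.1 states the hypothesis that intensified control will "positively affect the visual acuity in patients with DME and reduce the need for re-treatment".

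**The concern.** The hypothesis in 2.1 has two parts, and the injection count is the direct measure of the second, to "reduce the need for re-treatment". The plan gives no power for it. Variation between patients that baseline variables could explain stays in the error term of an unadjusted ANOVA. That widens the interval for the difference in injections and makes a real difference easier to miss.

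The data for an adjusted analysis already exist. Table 2 schedules laboratory tests (including HbA1c), BCVA, OCT and medical history at screening for every patient. The subgroup analyses of 6.1.6 do not do the same job: they split the sample and leave the overall comparison as it was.

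**Working it through.** **The plan's own figure.** Section 6.2 assumes a difference of 2.0 letters and an SD of 3.5, so d = 2.0/3.5 = 0.571, with two-sided alpha 5% and 85% power. The noncentral t distribution gives 85.0% power at 56 per arm and 84.4% at 55, so 56 per arm is confirmed. This figure is for the primary endpoint only.

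**Inputs for the count.** From the plan: N = 112 evaluable (120 randomised), 1:1 allocation, alpha 5% two-sided. Not in the plan, and therefore assumed: the standardised effect on the count (0.571 borrowed for illustration, and a smaller 0.4), and R, the multiple correlation of the four baseline variables with the count within arm (0 to 0.5).

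**Formula.** With q covariate degrees of freedom, the variance of the adjusted difference relative to the unadjusted one is

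(1 − R²) × (N − 3)/(N − q − 3).

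The second factor is the cost of chance covariate imbalance and must not be left out. With three continuous covariates and one yes/no covariate, q = 4. At N = 112 the factor is 109/105 = 1.038.

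**Break-even.** Adjustment helps when 1 − R² is below (N − q − 3)/(N − 3), that is, when R² exceeds q/(N − 3):
- N = 112: 4/109 = 3.7%
- N = 120: 4/117 = 3.4%
- HbA1c entered as three bands (q = 5): 5/109 = 4.6% and 5/117 = 4.3%

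So the threshold is about 3.5% with the four-term model, or R a little under 0.2.

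**Power at 56 per arm.** The unadjusted noncentrality is d√(n/2), which is 0.571 × √28 = 3.02, on 110 df. The adjusted noncentrality is that value divided by the square root of the variance ratio, on 106 df.

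| R | Variance ratio | SE ratio | Power, d = 0.571 | Power, d = 0.4 |
|---|---|---|---|---|
| unadjusted | 1 | 1 | 85.0% | 55.5% |
| 0 | 1.038 | 1.019 | 83.7% | 53.9% |
| 0.2 | 0.997 | 0.998 | 85.1% | 55.6% |
| 0.3 | 0.945 | 0.972 | 86.9% | 57.8% |
| 0.4 | 0.872 | 0.934 | 89.4% | 61.3% |
| 0.5 | 0.779 | 0.882 | 92.4% | 66.2% |

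For example, at R = 0.5 the ratio is 0.75 × 1.038 = 0.779. The adjusted noncentrality is 3.02/0.882 = 3.43.

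**Check by simulation.** The count was simulated as 3 scheduled injections plus up to 9 as-needed ones, with 60 per arm and 3,000 runs per scenario. Under no treatment effect the unadjusted ANOVA rejected in 4.5% to 5.4% of runs. Under an assumed effect, power unadjusted against adjusted was 78.1% against 77.7% with unrelated covariates (mean in-sample R² of 0.03, which is chance alone). It was 75.3% against 77.0% at R² of 0.10, 72.4% against 79.2% at 0.20, and 61.3% against 74.2% at 0.30. Direction and size agree with the formula.

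**The case against.** The strongest reply is that nothing here is an error. The unadjusted test holds its level under randomisation, the endpoint is secondary, and the trial is described as therapeutic-exploratory. The plan adjusts the BCVA analyses only for the outcome's own baseline, and a count has none. Its Cox model has no covariates either, and macular thickness is not baseline-adjusted. A four-covariate model would be richer than the primary one. All of this stands, and it keeps the point minor.

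It also stands that the loss is conditional. A reader might infer from 6.1.6 that precision is certainly lost. The documents do not support that. The label there is only potentially prognostic, is shared across several endpoints, and comes with no correlation with injections. Below break-even, adjustment slightly harms.

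A reader might also argue that the count is tied to baseline BCVA by design, because dosing follows BCVA. Section 4.6.1 does not support this either. Stopping and resuming depend on the BCVA course during treatment, and the first three injections are scheduled for everyone, which limits explainable variation, particularly at month 6.

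Nor is the lack of stratification a separate defect: the unadjusted standard error already allows for chance imbalance.

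What does not stand is that the choice is therefore a matter of taste. The possible gain is several times the possible loss, the variables were singled out by the plan itself, and 6.1.4 and the synopsis do not agree on the method.

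**Conclusion.** The point holds as one of efficiency. Section 6.1.4 excludes covariates from the comparison of the injection count, while the plan collects four baseline variables that it considers potentially prognostic for this endpoint among others. Precision is likely lost if they jointly explain more than about 3.5% of the variance of the count.

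Over the range examined at 56 per arm, adjustment changes power by −1.3 to +7.4 percentage points at d = 0.571 (83.7% and 92.4% against 85.0%), and by −1.6 to +10.7 points at d = 0.4 (53.9% and 66.2% against 55.5%). At R = 0.2 there is practically no difference. These figures rest on an assumed R and an assumed effect. The 0.571 belongs to the primary endpoint and says nothing about injections.

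The validity of the test, the primary analysis and the sample size are not affected.

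**What to change.** Before database lock, amend 6.1.4 or the SAP as follows:
- Analyse the injection count at each of months 6, 12, 18 and 24 by ANCOVA on treatment arm, baseline BCVA, baseline central retinal thickness and baseline HbA1c (all continuous), and ranibizumab before trial entry (yes/no).
- Report the adjusted difference in mean injections with its 95% confidence interval.
- Keep the unadjusted ANOVA as a supporting analysis.
- Bring the synopsis and 6.1.4 into agreement on the method for this endpoint.

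Fixing the covariates in advance also rules out choosing them after the results are seen.

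The cost is a sentence or two and one extra table, with no new data or visits. Statistically it is 4 degrees of freedom and, if the covariates turn out not to be prognostic, a standard error up to about 2% larger.

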4.4.1. Procedures for premature withdrawal from treatment during the trial

In case of patient withdrawal during the study period all data collected until this point of time will be stored according to AMG §40, 2a, 3. The patient must not be replaced.

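### Section 6.1.4 declares missing at random but fills BCVA and macular thickness by LOCF with no sensitivity analysis, and the thickness model leaves out baseline thickness

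*Combined protocol and SAP*

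**What the plan says.** Section 6.1.4 covers change in BCVA and macular thickness at 6, 12, 18 and 24 months in the ITT set. These data "are analysed by repeated measures analysis of variance (assuming missing at random, MAR"). The next sentence reads: "The missing values for BCVA and macular thickness are imputed by the last observation carried forward (LOCF"). Section 6.1.8 rules out imputation unless another section provides for it, so LOCF is a deliberate exception and would be carried out as written.

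Both models contain the arm-by-time interaction. Baseline enters only the BCVA model, "since the macular thickness will not be adjusted by the baseline value in this analysis". A separate paragraph of 6.1.4 summarises change from baseline in both variables descriptively.

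Section 6.1.6 plans two sensitivity analyses. The first is: "A sensitivity analysis for the primary endpoint based on the PP population will be performed". The second repeats the primary ANCOVA on log-transformed data.

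On leaving the trial, Section 4.4 introduces its list of reasons with "Study subjects will be early discontinued from participation in the study if". One reason is no reduction in central retinal thickness after three consecutive monthly injections; another is a loss of at least 30 letters. Section 4.6.8.1 adds: "If the therapeutic effect will be considered insufficient by either the patient or the treating physician the patient may be withdrawn from the study". For withdrawals, Section 4.4.1 says only that "all data collected until this point of time will be stored". A note in Section 4.4 points the other way: "Each patient should be followed-up even if the study treatment is discontinued".

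**The concern.** LOCF is not a way of carrying out an MAR analysis. It replaces MAR with the assumption that a patient's value stays where it was at the last visit. A likelihood-based repeated-measures model needs no imputation under MAR; after LOCF, MAR has nothing left to act on.

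The missing values can depend on the outcome. Persistent thickness and insufficient effect are both grounds for leaving the trial, so the values carried forward would tend to be poor ones, some from about month 3 and carried to month 24. The follow-up note in Section 4.4 limits such gaps but does not remove them. If dropout is substantial or differs between arms, the month 6 to 24 contrasts can be biased in either direction, and no planned analysis would show it.

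The omission of baseline thickness is a separate and milder matter. OCT is done at screening (Table 2), Section 6.1.6 lists edema size as potentially prognostic, and the BCVA model does use its baseline. The sentence in 6.1.4 restates the decision without giving a reason. The cost is wider confidence intervals for thickness.

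**Working it through.** **1. The plan's own figures.** Section 6.2 uses a difference of 2.0 letters, SD 3.5, two-sided alpha 5% and power 85%. The two-sample t-test gives 55.97, so 56 per arm (power 0.850). With the dropout allowance, 56 × 1.07 = 59.92, so 60. These figures reproduce and are not affected by this point. The allowance of about 7% is the only dropout figure in the documents, and it belongs to the month-12 primary endpoint.

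**2. What LOCF does.** In each arm,

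month-24 LOCF mean = true mean + Σ p_k × (mean carried from visit k − mean those patients would have had at month 24),

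where p_k is the proportion last seen at visit k. The arm contrast is unbiased only if this sum is equal in both arms. MAR does not ensure that.

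**3. Assumed inputs.** The documents give no thickness SD, within-patient correlation or dropout by arm, so all of these are assumptions:
- 60 per arm, SD 1, equal correlation ρ = 0.3, 0.5 or 0.7, 4000 replicates per scenario
- visits at baseline and months 3, 6, 12, 18, 24
- control means 0, −0.5, −0.7, −0.9, −1.0, −1.1
- arm effects 0, −0.05, −0.1, −0.2, −0.3, −0.4
- MAR dropout after months 3, 6, 12 and 18, with logit slope 0.8 per SD of the last observed value (thicker means more dropout)

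**4. Hand check on the means alone**, with dropouts spread equally over the four times and selection ignored. The average shortfall from the month-24 mean is (0.6 + 0.4 + 0.2 + 0.1)/4 = 0.325 in control. In the intensified arm (means −0.55, −0.8, −1.1, −1.3, −1.5) it is (0.95 + 0.7 + 0.4 + 0.2)/4 = 0.5625. The contrast is then −0.40 + 0.5625 × p(intensified) − 0.325 × p(control). For 10% control and 25% intensified: −0.40 + 0.141 − 0.033 = −0.292.

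**5. Simulated month-24 contrast (truth −0.40).**

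| Dropout control / intensified | Hand check | LOCF, ρ = 0.3 / 0.5 / 0.7 |
|---|---|---|
| 7% / 7% | −0.383 | −0.378 / −0.379 / −0.379 |
| 15% / 15% | −0.364 | −0.358 / −0.357 / −0.358 |
| 25% / 25% | −0.341 | −0.335 / −0.331 / −0.331 |
| 10% / 25% | −0.292 | −0.209 / −0.227 / −0.247 |
| 25% / 10% | −0.425 | −0.496 / −0.474 / −0.456 |

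With balanced dropout the means explain almost all of the bias. With unequal dropout, selection adds to it: thick last values would have regressed toward the mean, but LOCF freezes them, and more so at low correlation. A repeat run with 400,000 per arm agreed within about 0.01 (for example −0.203 / −0.221 / −0.240 at 10% / 25%). The maximum-likelihood mixed model (baseline by visit, unstructured covariance) gave −0.396 to −0.399 throughout, against −0.397 with complete data; this part was run once only.

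**6. A second set of assumptions, in letters** (SD 3.5, correlation 0.6, other mean profiles). A true month-24 difference of 2.0 became 1.92 at 7% dropout in both arms and 1.79 at 20%. With no true difference and 7% versus 20% dropout, LOCF produced a spurious difference of about −0.34 letters when means rise over time and about −0.07 when they are flat.

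**7. Baseline thickness.** Let ρ be the baseline to follow-up correlation, with equal variances. Adjusted over unadjusted variance is 1 − ρ² if raw thickness is the response. If change is the response it is (1 − ρ²)/[2(1 − ρ)] = (1 + ρ)/2.

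| ρ | Raw | Change |
|---|---|---|
| 0.3 | 0.91 | 0.65 |
| 0.5 | 0.75 | 0.75 |
| 0.7 | 0.51 | 0.85 |

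The standard error is multiplied by 0.95 to 0.71 (raw) or 0.81 to 0.92 (change). If the adjusted analysis had 85% power, the unadjusted one would have Φ(2.996 × √ratio − 1.960). That is 82%, 74% and 57% (raw) or 68%, 74% and 79% (change). Adding baseline to the LOCF analysis moved the estimate by at most 0.002, so baseline affects precision, not bias.

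**The case against.** The strongest reply concerns weight.

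- **Dropout level.** At the only rate the documents give, the bias is 0.02 SD at month 24 and below 0.01 SD at months 6 and 12. The larger figures need an imbalance that no section predicts, and Section 4.2 plans active follow-up by a dedicated nurse or physician. This stands as a limit on size. It does not make the rule coherent.
- **Time point.** Month 24 is the worst case. At 10% versus 25% the bias is about 0.03 to 0.045 SD at month 6 and 0.07 to 0.10 SD at month 12. Using the monthly visits of Tables 2 and 3 lowers the month-24 bias in that scenario by about 0.02 SD. Both points are fair.
- **Mixed model.** It recovers the truth because dropout was generated as MAR. That does not show MAR holds in this trial. It does show that LOCF can fail under the very assumption the plan declares.
- **Baseline.** An unadjusted comparison of randomised arms is valid, and in an exploratory trial leaving baseline out is inefficient, not wrong. That is agreed. The synopsis and Sections 2.3 and 4.7.1.2 also favour raw thickness as the response, though the sentence in 6.1.4 can be read either way.
- **Deferred detail.** Section 6.1 leaves further details to a statistical analysis plan, and no separate one is in the document reviewed. A sensitivity analysis could be added there, but removing LOCF or restoring baseline would contradict 6.1.4.

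**Conclusion.** The concern holds. Section 6.1.4 declares MAR and applies LOCF to the same data, and the supplied text has no sensitivity analysis for missing data in these endpoints. Under the assumed profiles the month-24 LOCF bias is about 0.02 SD at 7% dropout per arm and about 0.07 SD at 25% per arm. It is 0.15 to 0.19 SD toward zero when the intensified arm loses more patients (25% versus 10%), and 0.06 to 0.10 SD away from zero in the reverse case. These sizes are illustrative; the direction depends on which arm loses more patients.

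Leaving out baseline thickness loses precision without bias, by an amount that depends on an undocumented correlation. Only secondary endpoints are affected; the primary ANCOVA and the sample size stand. The change should be made, with high confidence in the finding.

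**What to change.** In Section 6.1.4:

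- Fit a likelihood-based mixed model for repeated measures to the observed data for both BCVA change and macular thickness, with arm, time, arm-by-time, baseline value and baseline-by-time. Include at least one visit before month 6 (for example month 3) among the responses, so that patients who leave early still inform the model.
- Delete the clause that excludes baseline for macular thickness, and state whether raw thickness or its change is the response.
- Drop LOCF, or keep it only as a labelled sensitivity analysis. One further analysis that departs from MAR would test the assumption the model then rests on.

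The cost is protocol and SAP wording. Baseline and follow-up BCVA and OCT are already collected, and neither the sample size nor the primary analysis changes.
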